15. STATISTICS

The Statistical Analysis Plan (SAP) will provide the details on the statistical methods planned for this study and will be finalized before the database lock of the study.

15.1. Sample Size

Approximately 120 subjects will be required for this study. This sample size was determined by the width of the 95% confidence interval for the proportion of subjects who may discontinue due to clinical reasons by Week 8 to ensure the precision of the estimate of the true discontinuation rate due to clinical reasons. Assuming, 1) 15% of SEP-363856 treated subjects will experience discontinuation due to clinical reasons by Week 8, and 2) 6.4% as the half width (the distance between the upper/lower limits to the point estimate) of the 95% confidence interval (ie, [8.6%, 21.4%]), approximately 120 subjects will be required.

15.2. Analysis Populations

15.2.1. Safety Population

The safety population will consist of all subjects who are enrolled and receive study medication. All safety and tolerability assessments will be performed using the safety population.

15.2.2. Effectiveness Population

The effectiveness population will consist of all subjects who are enrolled, have received at least one dose of study drug, and have a Baseline and at least one post-Baseline effectiveness measurement in PANSS or CGI-S. Subjects will be included in the population regardless of any protocol deviation. The effectiveness population will be the primary population for the effectiveness analyses.

15.3. Data Analysis

Descriptive statistics will be compiled for all endpoints.

15.3.1. Subject Disposition

Subject disposition will be summarized for all subjects. The number and percentage of subjects, who are screened, screen-failed, enrolled, received study drug, and completed or discontinued early from the open-label treatment period will be presented.

15.3.2. Study Drug Exposure and Compliance

Descriptive statistics on treatment exposure and treatment compliance will be summarized for the safety population.

Exposure, defined as number and percentage of subjects with ≥ 1 , ≥ 7 , ≥ 14 , ≥ 21 , ≥ 28 , ≥ 35 , ≥ 42 , ≥ 49 , and ≥ 56 days exposure, will be compiled. Descriptive statistics (n, mean, standard deviation, median, 25th and 75th percentile, minimum, and maximum) will also be calculated on exposure in days. Duration of exposure (in days) will be calculated as: last dose date - first study dose date + 1. An additional listing will also be generated to display the length of time that each subject received pre-switch anti-psychotic medication (with corresponding name and dosage).

Percent compliance will be calculated overall for the treatment period as: (number of capsules taken / number of capsules should have been taken) \times 100%. Non-compliance is defined as less than 75% or more than 125% non-missing compliance for the treatment period. Subjects with missing compliance will not be classified as non-compliant. Percent compliance will be summarized both as a continuous variable and categorically (ie. number and percentage of subjects in each compliance category: < 75%, 75% - 125%, > 125%, and missing).

Mean daily dose will be calculated for the treatment period as the cumulative dose (mg) of SEP-363856 divided by the duration of exposure (in days), where cumulative dose is the sum of all doses a subject received during the treatment period. Modal daily dose will be determined as the daily dose that is taken for the most time (in terms of number of days) among all doses taken. Both mean daily dose and modal daily dose will be summarized.

15.3.3. Important Protocol Deviations

Important protocol deviations (IPDs) will be identified and documented based on reviews of data listings and the protocol deviations log. The IPD categories may include, but may not be limited to:

- Did not satisfy important inclusion and/or exclusion criteria
- Received prohibited medication
- Overall compliance rate < 75% or > 125%.

IPDs will be identified for all enrolled subjects and presented in a data listing. The number and percentage of subjects within each IPD category will be summarized for the safety population.

15.3.4. Demographic and Baseline Characteristics

Basic demographics (eg, age, gender, race, ethnicity, etc.) will be summarized for all screened subjects. In addition, demographic and baseline characteristics will be summarized for each defined analysis population. Medical history will be coded using Medical Dictionary for Regulatory Activities (MedDRA) and will be summarized for the safety population by presenting the number and percentage of subjects with at least one condition in each system organ class (SOC) and preferred term (PT). Psychiatric history data will also be summarized for the safety population.

15.3.5. Safety Analyses

The primary analyses for this study will be performed for the safety endpoints, which are stated in [Section 6](#).

15.3.5.1. Primary and Secondary Endpoint Analysis

The primary endpoint is the percentage of subjects who discontinued for clinical reasons, such as due to AE or lack of efficacy. This percentage will be calculated by a proportion consisting of the number of subjects who experience a discontinuation event due to clinical reasons as the numerator divided by the number of subjects in the safety population as the denominator multiplied by 100 along with a corresponding 95% confidence interval (CI).

The secondary endpoint is the percentage of subjects who discontinued for any reason (ie, all cause discontinuation). The percentage will be calculated similarly as that of the primary endpoint along with a corresponding 95% CI.

The number and percentage of subjects, who discontinued early from the open-label treatment period (including both clinical reasons, ie, discontinued due to an AE (primary endpoint) and any reason for discontinuation (secondary endpoint)) will be presented.

As an exploratory analysis, the time-to-discontinuation for both clinical reason and for any reason will be summarized descriptively, (eg, n, median, 25th percentile, 75th percentile, minimum and maximum, and 95% CI on median, where possible) and presented with corresponding Kaplan-Meier plots.

15.3.5.2. Adverse Events

Both AEs and pre-treatment events will be coded using MedDRA.

The following summaries will be provided by MedDRA SOC and PT:

- All AEs (including incidence rate and event count)
- AEs by severity (mild, moderate, severe; including incidence rate)
- AEs by relationship to study drug (related, not related; including incidence rate)

The following conventions will be followed in summarizing AEs:

- For incidence rate summaries, each subject will be counted only once within each SOC and within each PT.
- If a subject reports more than one AE within a PT and/or a SOC, the AE with the highest known severity will be used in the by severity summary. AEs with a missing severity will be assigned to the highest severity.
- For summaries by relationship to study drug, AEs will be grouped as “related” or “not related.” AEs assessed as “possible,” “probable,” or “definite,” will be grouped as “related.” AEs with a missing relationship to study drug will be regarded as related. If a subject reports more than one AE within the same SOC and PT, and any are related, the AE will be summarized as related.

Summaries of serious AEs (SAEs) and AEs leading to discontinuation will also be provided. In addition, summaries of all AEs, SAEs, and AEs leading to discontinuation by modal daily dose will be provided. The summary of AEs will include any AE occurring on or after the first dose of study drug up to 9 days following the last dose of study drug. All AEs starting after the last dose of the study drug up to 9 days following the last dose will be summarized separately. Data listings of AEs, SAEs, AEs leading to discontinuation, and deaths will be presented.

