10.1.1. Dose Adjustment Criteria for SEP-363856

Subjects will receive SEP-363856 50 mg/day from Day 1 through Day 3 and 75 mg/day from Day 4 through Day 7. Every effort should be made to maintain subjects at 75 mg/day from Day 4 through Day 7. Beginning on Day 8, the dose of SEP-363856 can be adjusted in increments of 25 mg among 3 dose levels (50, 75 and 100 mg), according to the following requirements:

The SEP-363856 dose should be increased to 100 mg/day on Day 8 to help ensure adequate coverage of symptoms, provided there are no significant tolerability problems as judged by the Investigator. Dose increases are to be made no more frequently than weekly to the next highest dose level (in 25 mg increments). Increases in dose will occur at regularly scheduled study visits, when possible. Dose increases between regularly scheduled visits may occur after prospective approval by the Medical Monitor. If a dose increase is performed between regularly scheduled visits, subjects will be required to return to the clinic at an unscheduled visit for drug dispensation (see [Section 11.9.12](#)).

Beginning on Day 8, the SEP-363856 dose can be decreased at any time in 25 mg increments (including less than weekly intervals) as needed for safety or intolerance concerns as judged by the Investigator. If a dose decrease is needed between study visits, subjects will be asked to return to the clinic for an unscheduled visit for drug dispensation (see [Section 11.9.12](#)).

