3.7. CHANGES TO ANALYSIS FROM PROTOCOL

There are no changes to analysis from the protocol.

Document:	PPD		
Author:	PPD	Version Number:	1.0

Version Date: 06MAY2024

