14. STUDY MEDICATION EXPOSURE

Unless otherwise specified, the study medication exposure summary tables will include the column: SEP-363856 50 to 100 mg/day.

Exposure to study medication data will be summarized for the SAF population by the actual treatment group.

Duration of exposure (in days) will be summarized both as a continuous variable for the treatment period and categorically:

- Number and percentage of subjects with exposure $\geq 1, \geq 7, \geq 14, \geq 21, \geq 28, \geq 35, \geq 42, \geq 49$, and ≥ 56 days
- Number and percentage of subjects with exposure for 1 - 6, 7 - 13, 14 - 20, 21 - 27, 28 - 34, 35 - 41, 42 - 48, 49 - 55 and ≥ 56 days

Total person-years of exposure will be calculated for all subjects.

Mean daily dose and modal daily dose will be calculated for the treatment period and summarized.

The dose adjustment decision at each visit will be summarized in a shift table.

Lastly, the number of days that a subject received the 50 mg/day dose level, the 75 mg/day dose level and 100 mg/day dose level will be summarized for the SAF population both as a continuous variable and categorically:

- Number and percentage of subjects with exposure to a particular dose level for 1 - 6, 7 - 13, 14 - 20, 21 - 27, 28 - 34, 35 - 41, 42 - 48, 49 - 55 and ≥ 56 days

Document: PPD

Author: PPD

Version Number:

1.0

Version Date:

06MAY2024

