14.1. DERIVATIONS

- Duration of exposure (days) = date of last dose of study drug – date of first dose of study drug + 1. Interruptions in exposure (i.e., missed doses) and dose changes (if any) are not considered in the calculation of overall exposure.
- Total person-years of exposure is the sum of all durations of exposure in days / 365.25.
- Mean daily dose (mg/day):

$$\frac{\sum \text{Dose per tablet for Visit } j * (\# \text{ Tablets Dispensed for Visit } j - \# \text{ Tablets Returned for Visit } j - \# \text{ Tablets Lost for Visit } j)}{\text{Duration of Exposure}}$$

If the number of tablets dispensed, returned, and/or lost as collected on the "Study Treatment Administration as Collected / Drug Accountability Log" CRF form is missing for one or more visits, the mean daily dose will be calculated based on visits with complete drug accountability data available. That is, the numerator of the formula above will only include visits with the number of tablets dispensed, returned, and lost available, and the denominator should be adjusted to exclude dosing periods covered by visits excluded from the calculation (i.e., Duration of Exposure – dosing periods [sum of (EXENDTC – EXSTDTC+1)] covered by visits with missing or incomplete accountability data). If the dose level of a visit is unknown, that visit should be excluded from the calculation as well in both the numerator and the denominator.

- Modal daily dose will be determined as the daily dose that is taken for the most time (in terms of number of days) among all doses taken. A subject's modal daily dose may fall in one of the categories below:
 - SEP-363856 50 mg/day
 - SEP-363856 75 mg/day
 - SEP-363856 100 mg/day
 - Tie between xx and yy (i.e. the subject was on xx mg/day and yy mg/day for the same amount of time) (if needed)

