- In general, DOSEON/DOSEA should be the dose level immediately before the start of an AE or an assessment. In case the AE or the assessment start date/time coincides with the first dosing start date/time of the study, the DOSEON/DOSEA should be assigned to the dose level associated with that first dosing start date/time. In case the AE or the assessment start date/time coincides with a dosing start date/time other than the first dosing start date/time, the DOSEON/DOSEA should be assigned to the dose level associated with the previous dosing start date/time.
- In case of missing AE start time, missing assessment (start) time, and/or missing dosing start time, DOSEON/DOSEA should be assigned using the algorithm in the table below.

Scenario	Data	Rules
Dosing start date and start time both available	Adverse Events	If AE start date is available and AE start time is missing, dose on the same day as AE start should be assigned as DOSEON.
	Scales/Questionnaires, Vitals, Labs, ECG	If assessment start date is available and assessment start time is missing, dose on the previous day of the assessment should be assigned as DOSEA.
Dosing start date available but start time missing	Adverse Events	Regardless of whether AE start time is available, dose on the same day as AE start should be assigned as DOSEON.
	Scales/Questionnaires, Vitals, Labs, ECG	Regardless of whether assessment start time is available, dose on the previous day of the assessment should be assigned as DOSEA.

- In case of partial or missing AE start date, the imputed AE start date will be used for the purpose of assigning DOSEON.

Document: PPD

Author: PPD

Version Number:

1.0

Version Date:

06MAY2024

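### The table of AEs leading to discontinuation by modal daily dose favours 100 mg by construction, because subjects who stop by about Day 10 cannot be classed as modal 100 mg

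*Protocol*

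**What the plan says.** Protocol 15.3.5.2 commits to three sets of tables: "summaries of all AEs, SAEs, and AEs leading to discontinuation by modal daily dose will be provided". Protocol 15.3.2 and SAP 14.1 define modal daily dose as the dose taken on the largest number of days. SAP 14.1 adds, where needed, a category worded "Tie between xx and yy".

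Dosing in the first week is fixed (Protocol 10.1.1): "Subjects will receive SEP-363856 50 mg/day from Day 1 through Day 3 and 75 mg/day from Day 4 through Day 7". The next step is "The SEP-363856 dose should be increased to 100 mg/day on Day 8 to help ensure adequate coverage of symptoms", subject to the investigator seeing no significant tolerability problem. Reductions for safety or intolerance are allowed from Day 8. The Day 8 visit has a window of +2 days (Protocol Table 2, note e).

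The text of SAP 17.3 lists no AE table by modal dose, yet SAP 3.7 says "There are no changes to analysis from the protocol". The SAP does define a dose-at-onset variable in Appendix 2: "DOSEON/DOSEA should be the dose level immediately before the start of an AE or an assessment". SAP 14 also summarizes "the number of days that a subject received the 50 mg/day dose level, the 75 mg/day dose level and 100 mg/day dose level". The text of SAP 17.3 names no table that uses the dose-at-onset variable.

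**The concern.** Modal dose is known only when treatment ends, and the outcome helps to determine it. A subject who stops early for an AE has had no time to accumulate a majority of days at 100 mg, even if the AE began on 100 mg. A subject who tolerates 100 mg poorly may be reduced, or never raised, and is then counted at a lower dose. In the table of AEs leading to discontinuation, both routes move events out of the 100 mg column.

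Tolerability at 100 mg is a live question in this programme. Protocol 7.3.2 records 75 mg/day as the multiple-dose MTD, after 5 of 9 subjects at 100 mg/day had multiple moderate related AEs. A table that leans towards 100 mg by construction could mislead on exactly that point.

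**Working it through.** The documents give no figure for these tables, so there is nothing of the plan's own to reproduce. The nearest anchor is the clinical discontinuation rate of about 7.2% in SAP 3.4, which combines AEs and lack of efficacy.

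**1. When can 100 mg be the modal dose?** Let *u* be the day of the increase to 100 mg and *L* the last-dose day. Days at 50 mg are 3, days at 75 mg are *u* − 4, and days at 100 mg are *L* − *u* + 1. So 100 mg is the sole mode when *L* − *u* + 1 > *u* − 4, that is, *L* > 2*u* − 5.

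- *u* = 8: the mode is 50 mg for last dose on Days 1-5, a 50/75 tie on Day 6, 75 mg on Days 7-10, a 75/100 tie on Day 11, and 100 mg from Day 12.
- *u* = 10 (end of the visit window): 75 mg through Day 14, a tie on Day 15, and 100 mg from Day 16.

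**2. Dose reduction.** Take a subject on 100 mg from Day 8, reduced to 75 mg on Day *r*, who completes to Day 56. Days at 100 mg are *r* − 8; days at 75 mg are 4 + (57 − *r*). The mode is 75 mg when *r* − 8 < 61 − *r*, so for *r* up to 34 (Day 34: 26 days against 27).

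**3. Size of the false gradient.** Assumptions, none from the documents: 1,000 subjects; a 7% risk of stopping for an AE, unrelated to dose; 15% stay at 75 mg and 85% go to 100 mg on Day 8; no reductions; ties kept as their own category. Of the 930 completers, 790.5 are at 100 mg and 139.5 at 75 mg. Of the 70 who stop:

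| Timing of the 70 | Modal 75 mg | Modal 100 mg |
|---|---|---|
| Flat over Days 1-55 | 70×4/55 + 0.15×70×45/55 = 13.68; 13.68/153.18 = 8.9% | 0.85×70×44/55 = 47.6; 47.6/838.1 = 5.7% |
| Half in Days 1-11, half in Days 12-55 | 35×4/11 + 0.15×(35/11 + 35) = 18.45; 18.45/157.95 = 11.7% | 0.85×35 = 29.75; 29.75/820.25 = 3.6% |

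Each denominator is completers plus discontinuers in that column. The true risk is 7% in every row. With overall risk at 7.2% and 50% to 90% of subjects raised to 100 mg, simulation gives about 4% to 6% at 100 mg and 8% to 27% in the 50/75 mg groups combined.

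**4. Does dose at onset remove it?** In the front-loaded scenario of step 3:

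| Dose at onset | Events / person-days | Per 100 person-days |
|---|---|---|
| 50 mg, all days | 9.55 / 2,990 | 0.32 |
| 75 mg, all days | 19.89 / 10,922 | 0.18 |
| 100 mg, all days | 40.57 / 39,550 | 0.10 |
| 75 mg, from Day 8 | 7.16 / 6,979 | 0.10 |
| 100 mg, from Day 8 | 40.57 / 39,550 | 0.10 |

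Without a split by time, a threefold gradient remains, because the lower doses are taken in the high-risk first days. From Day 8 the two doses agree, as they should when dose has no effect.

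**The case against.** The strongest reply is that these are descriptive tables with little weight. No dose comparison is planned (SAP 7.1, 7.4), the primary endpoint is not split by dose, and SAP 17.1 shows time to discontinuation separately. No section says that the modal-dose tables will support a conclusion about dose. That stands, and it limits the consequence.

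A reader might infer that every early discontinuer lands in a low-dose group. The documents do not support this. Protocol Table 4 counts anyone who does not complete the treatment period as an early termination. If all are raised on Day 8, 80% of discontinuers would be modal 100 mg with last-dose days uniform over Days 1-55 (44/55), and 33% with a 7-day half-life. Only those who stop by about Day 10 are forced low.

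A reader might also infer that all three tables make 100 mg look safer. For all AEs and SAEs, the 100 mg group has longer exposure and also carries events that began on 50 or 75 mg, both of which raise its incidence. The net direction is not fixed.

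Nor should the 50 mg column be read as showing a rate of 100%. It does so in step 3 only because nobody is assumed to be reduced to 50 mg and stay there. With the 101 subjects enrolled, it would hold about 0.6 to 1.6 people (6.36 or 15.91 per 1,000).

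Two objections to possible remedies also stand. Dose at onset alone still shows a gradient when risk is front-loaded. Restricting the modal-dose table to subjects treated for at least 14 days would delete the early AE discontinuers from a safety table. Finally, SAP 8 refers to output templates that are not among the documents, so the absence of modal-dose or DOSEON tables can be stated only for the SAP text.

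**Conclusion.** The concern holds for the table of AEs leading to discontinuation. That early stoppers cannot be modal 100 mg follows from the dosing schedule and the definition of modal dose, with no further assumption. The size, about 9% to 12% at 75 mg against 4% to 6% at 100 mg with no dose effect, rests on the assumed 7% risk, the 15% staying at 75 mg, the increase on Day 8 and the two timing patterns. The 7% may be high, since the SAP's 7.2% includes lack of efficacy. The all-AE and SAE tables attribute events to the wrong dose, without a fixed direction. The primary and secondary endpoints are untouched.

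Separately, Protocol 15.3.5.2 requires tables that the text of SAP 17.3 does not list, while SAP 3.7 reports no change. This needs reconciling whatever view is taken of the bias. The change should be made, but the trial's main conclusion does not depend on it.

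**What to change.** For AEs leading to discontinuation, and preferably also for all AEs and SAEs, tabulate by dose at onset (DOSEON, SAP Appendix 2) per 100 person-days at that dose (days at each dose level, SAP 14). Show Days 1-7 and Day 8 onward separately. The split keeps dose from being confounded with the titration week, which is also the week on the full pre-switch antipsychotic dose.

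If the modal-dose tables are kept, add a footnote that subjects stopping by about Day 10 (up to Days 14-15 with the visit window) cannot be modal 100 mg. Do not restrict them to subjects with at least 14 days of treatment.

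Reconcile Protocol 15.3.5.2 with SAP 17.3 and record the change in SAP 3.7.

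The cost is one extra table from data that the SAP already derives, and one listed departure from the protocol. Dose from Day 8 still depends on tolerability, so the new table remains descriptive and does not estimate a dose effect.

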15.3.5.3. Clinical Laboratory Assessments

Clinical laboratory parameters will be summarized by presenting shift tables and by-visit summaries of the observed values including the Week 8 last observation carried formula (LOCF) Endpoint along with change from Baseline values. For parameters with categorical outcomes, the number and percentage of subjects with each outcome will be summarized by visit. The number

and percentage of subjects with at least one potentially clinically significant (PCS) value post Baseline for selected parameters will also be presented. PCS criteria for clinical laboratory parameters will be provided in the SAP.

15.3.5.4. ECGs

ECG analysis will be based on the centrally read data. Observed values and changes from Baseline in ECG parameters will be summarized along with shift in ECG overall assessment. In addition, the number and percentage of subjects with prolonged QTc intervals (> 450 msec, > 480 msec, and > 500 msec) and changes in QTc intervals ≥ 30 but < 60 msec and ≥ 60 msec will be summarized. Fridericia's correction (QTcF) and Bazett's correction (QTcB) will be used for QT interval correction.

